7.3.3 Evaluations at Enrollment (Baseline)

- Determine whether the subject's maintenance asthma medications are in accordance with conventional therapy utilizing inhaled corticosteroids and long-acting β_2 -agonists appropriate for the severity of the Subject's asthma.

Subjects who require a medication adjustment in order to optimize asthma control must undergo a 4-week medication stabilization period prior to performing enrollment evaluations. If the subject's maintenance asthma medications ARE in accordance with conventional therapy and subject has been on stable asthma medications for at least four weeks:

- Administer Asthma Quality of Life Questionnaire (AQLQ).
- Obtain detailed medical history, to include:
 - Gender
 - Race
 - Date of birth
 - Number of years diagnosed with asthma
 - History of allergies, to include allergy type and the time of year they are susceptible
 - History of respiratory infections in the 2 years prior to the study
 - Other significant illnesses
- Obtain history of asthma symptoms, exacerbations, and asthma medications, to include:
 - Number of emergency room visits for respiratory symptoms over the past 12 months
 - Number of hospitalizations for respiratory symptoms over the past 12 months
 - Number of pulses of systemic corticosteroids (tablet, suspension, or injection) for asthma symptoms over the past 12 months
 - Number of Intensive Care Unit (ICU) admissions for asthma symptoms over lifetime, and timing of each such admission
 - Changes in maintenance asthma medications, if any
- Perform pre-bronchodilator spirometry following a 12-hour abstinence from long-acting β_2 -agonist and a 4-hour abstinence from short-acting β_2 -agonists.
- Perform post-bronchodilator spirometry 15 minutes after the administration of 4 puffs (100 μ g per puff) of albuterol via a spacer.
- Perform the following evaluations:
 - Physical examination, including body weight, vital signs, pulse oximetry (SpO_2) and breath sounds.
 - Blood coagulation panel and Complete Blood Count (CBC)
 - Pregnancy test for female subjects of childbearing potential (a positive pregnancy test at this time will disqualify the subject from the study).
 - Obtain Chest X-rays – lateral and posterior anterior (PA) views. Chest X-rays performed within the last 4 months may be used.

- If all entry criteria have been met, enroll the subject and schedule their first bronchoscopy session.

NOTES:

1. *If the subject has an exacerbation during the period of enrollment evaluations that is treated with oral steroids, wait at least 4 weeks following completion of the oral steroids, before proceeding with any further evaluations.*
2. *During the period between enrollment and the entire study period out to 5 years, all subjects should continue to take the same dose, route, and frequency of inhaled corticosteroids, LABA, and other maintenance asthma medications prescribed prior to enrollment. In the instance that medications are adjusted for patient safety, record any deviations from this specified medication usage in the subject's medical chart and on CRF/eCRFs during subsequent follow-up visits.*

Provide the following specific instructions to all subjects that are enrolled in the study:

1. It is important to complete all scheduled study visits and respond to telephone contacts by the research team.
2. It is important to contact the Investigator or the research team if the subject experiences worsening of their asthma symptoms beyond their normal level of symptoms.
3. It is important to seek medical attention between scheduled study visits if necessary.
4. For the periods between scheduled study visits or telephone contacts, subjects should be encouraged to keep track of any adverse events, pulses of oral corticosteroids for worsening of asthma symptoms, emergency room visits for respiratory symptoms or hospitalizations for respiratory symptoms in a diary or log. For any event, subjects' should note the date event occurred, any treatment that was used to address the event, and the date the event was considered resolved. This will aid in an unbiased recall of events.
5. These instructions should be reinforced during each contact with a study subject.

7.3.4 Prior to Performing Bronchial Thermoplasty with the Alair System

- Ensure that subject has not had an asthma exacerbation that was treated with systemic corticosteroids within the last two weeks.

Do not schedule the treatment session if the subject had an asthma exacerbation requiring systemic corticosteroids within the last 2 weeks and their post-bronchodilator FEV₁ is not back to within 10% of baseline/enrollment levels.

- Ensure that subject has not had a lower respiratory tract infection within the last six weeks.

Do not schedule the treatment session if the subject had a lower respiratory tract infection that resolved within the last 6 weeks.

- Ensure that subject has not had an upper respiratory tract infection within the last one (1) week.

Do not schedule the treatment session sooner than one (1) week after resolution of symptoms from a recent upper respiratory tract infection.

- Prescribe 5 doses of 50mg each of oral prednisone or equivalent to be taken on the three days prior to treatment, day of treatment, and day after treatment (prophylactic indication).

Document in subject's study notes and treatment-related CRF/eCRFs; do not add as an additional concomitant medication.

- Schedule the treatment session to allow for required minimum of 4 hours monitoring of subject prior to discharge.
- Subject must continue taking their maintenance asthma medications of inhaled corticosteroids and LABA as prescribed.
- If antibiotics are prescribed for prophylaxis according to institutional policies at the time of the treatment, the antibiotic usage should be noted on the Medication Log for this subject, but this use of antibiotics will NOT trigger the actions called for in Section 8.0 Adverse Events, with regard to infections.

7.3.5 Bronchial Thermoplasty Treatment

Bronchial thermoplasty with the Alair System will be performed in three bronchoscopy sessions, separated by at least 3 weeks. The areas targeted for treatment with the Alair System are the airways distal to the main stem bronchi (beginning at the lobar bronchi, 2nd Weibel generation) down to airways of 3mm in diameter (about the 6th Weibel generation).

- During the first bronchoscopy session, the right lower lobe (RLL) will be treated.
- During the second bronchoscopy session, the left lower lobe (LLL) will be treated.
- During the third bronchoscopy session, both the right upper lobe (RUL) and the left upper lobe (LUL) will be treated.
- The right middle lobe (RML) will not be treated (see Section 7.3.7).

After the first bronchoscopy session and at all subsequent bronchoscopy sessions, carefully conduct a visual bronchoscopic examination of previously treated airways and document any findings. If any clinically significant findings are observed, subsequent bronchoscopy session should be postponed for at least two weeks and until the subject is clinically stable. At the subsequent bronchoscopy the previously abnormal area should be re-inspected. Complete resolution of any findings must be confirmed and documented in the subject's medical records before subsequent Alair treatments commence. If the abnormal findings persist, Investigator should consult with Sponsor to determine whether to proceed with

further treatments or abandon further treatments. In the event that further treatments are not performed, the subject should remain in the study for continued follow-up.

7.3.6 Pre-Procedure Evaluations

- Determine if subject has recently had, or is currently experiencing cold or respiratory symptoms.

If subject has recently had or is currently experiencing cold or respiratory symptoms, the treatment session must be rescheduled until the subject no longer has these symptoms. Inform subject that the chance of post-procedure side effects increases under these circumstances.

- Verify that the subject has taken the prescribed 50mg oral prednisone or equivalent per day, for the three days prior to, and on the day of treatment session (prophylactic indication).

If the prescribed prednisone or equivalent was not taken on the three days prior to bronchoscopy, the treatment should be postponed. If the dose of prednisone or equivalent was not taken for the day of the treatment session, an equivalent dose may be given intravenously during the procedure or just after the procedure and prior to release.

- Perform a pregnancy test for female subjects of child bearing potential
 - A positive pregnancy test before the first bronchoscopy session will disqualify the subject from the study.
 - A positive pregnancy test prior to the second bronchoscopy session will result in termination of further bronchoscopy procedures for the subject. However, the subject must be evaluated as per protocol at all planned evaluation visits.
- Perform a post-bronchodilator FEV₁

Postpone treatment session if any of the following conditions apply:

- a. Prescribed prednisone or equivalent was not taken on the three days prior to treatment.
- b. SpO₂ less than 90% on room air in last 48 hours.
- c. Increase in asthma symptoms in last 48 hours requiring more than 4 puffs/day of rescue bronchodilator over normal usage.
- d. Subject is less than 2 weeks from completion of a course of oral corticosteroid use for an exacerbation of asthma.
- e. Subject's post-bronchodilator FEV₁ is less than 85% of baseline/enrollment level.
- f. Subject has an active respiratory infection, active allergic sinusitis, or other clinical instability.
- g. Investigator feels for any reason the treatment should be postponed.
- h. The absence of a companion or caretaker at home to assist on the day of treatment.

7.3.7 Bronchoscopy Session

If bronchoscopy session is not postponed for any of the above criteria:

- Prepare subject for bronchoscopy per standard hospital protocol.
- Review the treatment plan, including previously treated anatomy (if applicable), identifying targeted anatomy, and choosing the sequence of segments to be treated.
- Administer up to 5 mg albuterol (short-acting bronchodilator), nebulized.
- Administer IV moderate sedation to perform bronchial thermoplasty. During the period of sedation, monitoring should be performed to include at a minimum, SpO₂, heart rate, blood pressure, and ECG. All local institutional policies relevant to moderate sedation should be observed.
- The use of a drying agent such as atropine or glycopyrrolate to reduce secretions is recommended for this procedure.

Criteria for considering termination of a bronchoscopy based on bronchoscopic findings:

- a. Airways are unusually edematous or inflamed.
- b. Extensive and/or prolonged bronchoconstriction.
- c. Airways accessed in a previous treatment session do not appear sufficiently healed.
- d. Presence of purulent or abnormally tenacious sputum or mucus plugging.
- e. Inability to access airways because of excessive secretions, excessive coughing, or tortuous anatomy.
- f. Investigator feels for any reason the treatment should be terminated.

- Perform Bronchial Thermoplasty as follows:
 - Apply the return electrode to subject (lower back suggested).
 - Attach the Alair Catheter to the Alair RF Controller.
 - If the procedure is the second or third bronchoscopy session, carefully examine previously treated airways with the bronchoscope.

Complete resolution of any findings must be documented before any subsequent Alair treatments commence. Do not treat airways that were treated in a previous treatment session.

- Do not treat the Right Middle Lobe. The right middle lobe is not treated because of the potential theoretical susceptibility of the right middle lobe to transient obstruction as a result of inflammation or edema because of certain anatomical characteristics. This area had not been treated in previous clinical trials of the Alair System and therefore will not be treated here for consistency.
- Advance the bronchoscope to the desired airway and insert the Alair Catheter through the working channel of the bronchoscope. Expand the electrode array to contact the airway wall.
- Activate the RF Controller by pressing the footswitch and deliver RF energy to the target site.
- Collapse the electrode array and reposition the electrode array 5 mm proximally from the previous location. Repeat the delivery of RF energy.
- Continue with treating the length of the airway with contiguous placements and activations of the electrode array.

NOTE: It is expected that each subject will undergo three treatment sessions. If during the first treatment a subject's airways are noted to be unusually small, tortuous, or of such atypical anatomy that either a safe or a complete procedure cannot be performed, do not proceed with treatment; the subject should be withdrawn from the study.

7.3.8 Post-Bronchoscopy Monitoring and Evaluation

Carefully monitor the subject in the post-procedure recovery area for at least 4 hours as follows:

- Perform at least two assessments of vital signs (heart rate, blood pressure, temperature, respiratory rate, SpO₂): the first within one hour of the treatment; the second just prior to discharge. Perform additional assessments if medically indicated.
- Administer supplemental oxygen if clinically indicated or if SpO₂ falls below 92% (via facemask or nasal cannula). Record the use of supplemental oxygen and reason for administration.
- Assess spirometry and breath sounds at least twice: as soon as the subject has recovered from sedation/anesthesia and just prior to discharge. Perform additional assessments if medically indicated. Record bronchodilators administered during spirometry.
- Document any adverse events (See Section 8.0).
- Document hospital admission if necessary.

Criteria for considering hospital admission post-procedure:

- a. Severe or persistent cough at end of monitoring period.
- b. Failure of post-bronchodilator FEV₁ to return to within 20% of pre-procedure level at end of monitoring period.
- c. Persistent oxygen saturation <90% at end of monitoring period.
- d. Persistent tachycardia >130bpm at end of monitoring period.
- e. Unexpected altered mental status during or after procedure.
- f. Hemoptysis >50ml during 4 hour post-recovery period.
- g. Excessive requirement for bronchodilator during monitoring period.
- h. The absence of a companion or caretaker at home to assist on the day of treatment.

NOTE: Overnight hospitalizations for observational reasons will not be considered as Serious Adverse Events, but will be tracked as Adverse Events.

Prior to discharge after each bronchoscopy session:

- Remind subject to take 50mg oral prednisone, or equivalent, the day after the treatment session (prophylactic indication).
- Schedule a follow-up evaluation for 2 weeks after each treatment session.
- Instruct subject to contact Investigator or a member of the clinical study staff at the Site if they experience any of the following:
 - Difficulty in breathing.
 - Night awakenings due to asthma symptoms.
 - Changes in maintenance asthma medications.
 - Need to be seen by a physician prior to the next scheduled visit.
 - Any adverse events.
- Record Date and Time of release after the procedure from facility.

7.3.9 Near-Term Follow-up

- Contact subject via telephone on Day 1, Day 2, and Day 7 after the treatment session to assess recovery.
- Remind subject to contact Investigator or a member of the clinical study staff at the Site if they experience any of the following:
 - Difficulty in breathing.
 - Night awakenings due to asthma symptoms.
 - Any changes in maintenance asthma medications.
 - Need to be seen by a physician prior to the next scheduled visit.
 - Any adverse events.

7.3.10 2-Week Follow-up (2 Weeks \pm 4 days after Treatment Session 1 and 2)

Examine the subject and perform the following evaluations:

- Focused physical exam including vital signs (heart rate, blood pressure, temperature, respiratory rate, SpO₂) and breath sounds.
- Review asthma symptoms, exacerbations, and asthma medication use.
- Solicit adverse events since last follow-up (See Section 8.0).
- Review Emergency Room visits for respiratory symptoms since last contact.
- Review hospitalizations for respiratory symptoms since last contact.
- Perform physical examination (including body weight).
- Pre-bronchodilator spirometry following a 12-hour abstinence from long-acting β_2 -agonist and a 4-hour abstinence from short-acting β_2 -agonists
- Post-bronchodilator spirometry 15 minutes after the administration of 4 puffs (total 400 μ g) of albuterol via spacer.
- If a subsequent treatment session is to be completed, see Section 7.3.6 and Section 7.3.7.

7.3.11 6-Week Follow-up (6 Weeks \pm 1 Week after last Bronchoscopy Session)

Examine the subject and perform the following evaluations:

- Focused physical exam including body weight, vital signs (heart rate, blood pressure, temperature, respiratory rate, SpO₂) and breath sounds.
- Review asthma symptoms, exacerbations, and asthma medication use.
- Solicit adverse events since last contact.
- Perform pre- and post-bronchodilator spirometry. Pre-bronchodilator spirometry following a 12-hour abstinence from long-acting β_2 -agonist and a 4-hour abstinence from short-acting β_2 -agonists.
- Review emergency room visits for respiratory symptoms since last contact.
- Review any hospitalizations for respiratory symptoms since last contact.

7.3.12 3-Monthly Follow-up Phone Contact (3 Months \pm 2 Weeks, 6 Months \pm 2 Weeks, 9 Months \pm 2 Weeks, 15 Months \pm 2 Weeks, and 18 Months \pm 2 Weeks, 21 Months \pm 2 Weeks, 27 Months \pm 2 Weeks, 30 Months \pm 2 Weeks, 33 Months \pm 2 Weeks, 39 Months \pm 2 Weeks, 42 Months \pm 2 Weeks, 45 Months \pm 2 Weeks, 51 Months \pm 2 Weeks and 54 Months \pm 2 Weeks, and 57 Months \pm 2 Weeks after 6-Week Follow-up Evaluation)

Perform the following evaluations:

- Review asthma symptoms, exacerbations, and asthma medication use.
- Solicit adverse events since last follow-up (See Section 8.0).
- Review emergency room visits for respiratory symptoms since last contact.
- Review any hospitalizations for respiratory symptoms since last contact.

7.3.13 Yearly Follow-up (12 Months \pm 4 Weeks, 24 Months \pm 4 Weeks, 36 Months \pm 4 Weeks, 48 Months \pm 4 Weeks and 60 Months \pm 4 Weeks after 6-Week Follow-up Evaluation)

Examine the subject and perform the following evaluations:

- Perform physical exam including body weight, vital signs, pulse oximetry and breath sounds.
- Review asthma symptoms, exacerbations, and asthma medication use.
- Solicit adverse events since last contact.
- Perform pre- and post-bronchodilator spirometry. Pre-bronchodilator spirometry following a 12-hour abstinence from long-acting β_2 -agonist and a 4-hour abstinence from short-acting β_2 -agonists.
- Review emergency room visits for respiratory symptoms since last contact.
- Review any hospitalizations for respiratory symptoms since last contact.

7.3.14 Study Exit

Exit the subject from the study following the successful completion of the 5 year follow-up evaluation.

8.0 Adverse Events

Definition: An adverse event is any sign, symptom, illness, clinically significant abnormal laboratory value, or other adverse medical event that appears or worsens in a subject during a clinical study, regardless of whether or not it is considered related to the procedure used as part of the protocol.

- It is the responsibility of the Investigator to decide when an adverse event has occurred.
- Adverse event information will be collected throughout the study.
- Adverse events will be recorded on the Adverse Event CRF/eCRF by the Investigator or clinical study staff and must include
 - Diagnosis
 - Symptoms
 - Date of onset
 - Date of resolution
 - Severity
 - Relationship to the procedure
- All adverse events will be monitored until they are adequately resolved or stabilized with no further significant change expected.

All Serious Adverse Events or complications must be reported to Clinical Affairs at Asthmatx, Inc. within 3 working days via

Telephone: [name]

FAX: [name], or

E-mail: [contact]

For all Serious Adverse Events, reports relating to the subject's subsequent medical follow-up must be submitted to Sponsor until the event has subsided or, in case of permanent impairment, until the event stabilizes and the overall clinical outcome has been ascertained.

Asthmatx Clinical Affairs will perform real time data review to observe any unanticipated or unforeseen events and to monitor the actual rate of anticipated events. All events will be MedDRA coded and entered into a database for later analyses. This review will occur on an ongoing basis upon event notification.

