6.7 Data collection and Follow-up schedule

The planned study visits are outlined in the Study Flow Chart shown in Figure 2.

All data will be collected using appropriately designed case report forms (CRFs/eCRFs). Information on adverse events, incidences of OCS pulses for worsening of asthma symptoms, emergency room visits for respiratory symptoms, and hospitalizations for respiratory symptoms will be actively solicited by an appropriately qualified member of the clinical study site team during quarterly telephone contacts or at time of in-office visits.

Daily diaries will not be used in this clinical study, and all information solicited from the study subjects will be based on recall since the last contact (maximum recall time of 3 months). Episodes of worsening of asthma symptoms requiring treatment with oral corticosteroids, emergency room visits and hospitalizations for respiratory symptoms are rare events and are readily recalled for immediate past periods of 3 month duration. This approach will be consistent with data collection methodology in the AIR2 Trial.

The following data will be collected at the specified visits/evaluations:

Enrollment

- Medical history (including maintenance asthma medications and history of respiratory infections)
- Occurrence of events in the 12 month period prior to study enrollment
 - Severe exacerbations (pulses of systemic corticosteroids (tablets, suspension, or injection) for asthma symptoms)
 - Emergency room visits for asthma symptoms
 - Hospitalizations for asthma symptoms
- Forced Expiratory Volume in 1 second: FEV₁ (pre- and post-bronchodilator)
- Physical examination (including body weight)
- Chest X-ray (Lateral and PA)
- Asthma Quality of Life Questionnaire (AQLQ)

Treatment Period (Day of 1st bronchoscopy till 6 weeks after 3rd/last bronchoscopy)

- Adverse events
- Emergency room visits for respiratory symptoms
- Hospitalizations for respiratory symptoms
- FEV₁ (pre- and post-bronchodilator)

Phone Contact at every 3 Months between Annual Visits

- Adverse events
- Severe exacerbations
- Maintenance asthma medications
- Emergency room visits for respiratory symptoms
- Hospitalizations for respiratory symptoms

Annual Visits at 1, 2, 3, 4 and 5 years from end of Treatment Period (6 week visit following 3rd/last bronchoscopy)

- Adverse Events
- Severe exacerbations
- Physical examination (including body weight)
- Maintenance asthma medications

- Emergency room visits for respiratory symptoms

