8.1 Definitions

A. Severe Exacerbation: Severe exacerbation defined as worsening of asthma symptoms requiring use of systemic corticosteroids (tablets, suspension, or injection) (NAEPP, 2007). For subjects already taking oral corticosteroids on a daily or alternate day basis, a severe exacerbation will be defined as a worsening of asthma symptoms requiring any increase in daily dose of systemic corticosteroids.

For consistency, courses of corticosteroids separated by 1 week or more will be treated as separate severe exacerbations.

B. Severity of Adverse Events: The following definitions for rating severity of adverse events should be used for this study:

1. **Mild:** Awareness of signs or symptoms, but easily tolerated and transient; causing no loss of time from normal activities; symptoms would not require medication (other than short-acting bronchodilators) or a medical treatment; signs and symptoms are transient.
2. **Moderate:** Marked symptoms and discomfort severe enough to cause moderate interference with subject's usual activities. Symptomatic treatment is possible.
3. **Severe:** Incapacitating with inability to do work or usual activities; signs and symptoms may be of systemic nature or require medical intervention and/or treatment. Hospitalization may be required or prolonged.

The Investigator will determine both the intensity of the adverse event and the event's relationship to Alair treatment. The Data and Safety Monitoring Board (DSMB) will review all respiratory adverse events and other safety endpoint data including hospitalization for respiratory symptom and review procedure/device relationship.

C. Serious Adverse Events (SAE): All adverse events are categorized as Mild, Moderate or Severe (see Section B above). Additionally, if an adverse event meets any of the following criteria, it is also categorized as an SAE when the event is:

- Fatal
- Requires or prolongs hospitalization
- Causes substantial risk of dying at the time of the event (i.e., life-threatening)
- Results in permanent impairment of a body function or permanent damage to a body structure, or
- Requires medical or surgical intervention to prevent permanent impairment of a body function or permanent damage to a body structure
- Results in fetal distress, fetal death or congenital abnormality or birth defect

Note: This categorization for adverse events is independent of the severity rating applied above in Section B.

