2 ENDPOINT ANALYSIS

2.1 Primary Endpoint

The primary endpoint will be the proportion of subjects experiencing severe exacerbations during the subsequent 12-month period (for Years 2, 3, 4, and 5) compared to the first 12-month period after the Alair treatment.

Note: Severe exacerbation is defined as worsening of asthma symptoms requiring use of systemic corticosteroids (tablets, suspension, or injection). For subjects already taking oral corticosteroids on a daily or alternate day basis, a severe exacerbation will be defined as a worsening of asthma symptoms requiring any increase in daily dose of systemic corticosteroids. For consistency, courses of corticosteroids separated by 1 week or more will be treated as separate severe exacerbations.

The primary statistical objective is to demonstrate that the proportion of subjects who experience severe exacerbations in the subsequent 12-month follow-up (for Year 2, Year 3, Year 4 and Year 5 [in 12-month periods]) is not statistically worse when compared with the proportion of the first 12-months, which begins 6 weeks after the last Alair treatment. This objective will be met if the upper 95% confidence limit of the difference in proportions (i.e., the subsequent 12-month proportion minus the first 12-month proportion) is less than 20%.

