6.4 Identification of Severe Exacerbations (SE)

1. Filter the medication data (MEDS) to keep all courses of oral corticosteroids (CLASS3=OCS) and other medications that are intravenous uses of the same medications - identify those by looking for CLASS3='Other Specify' and lowercase(CLSSP) with values: 'intravenous corticosteriod' 'intravenous corticosteroid' 'cortcosteroid iv' 'corticosteroid iv'. Note there are spelling mistakes in the entered data.
2. Merge the medication data with the AE data by patient and AE related number (RELAENO) on the medication data with AENUM on the AE data.
3. Use the onset date and the resolution date of the AE to determine the length of the SE. If an AE has no resolution date, impute the date of the most recent follow-up (scheduled or

Study Reference Number E7080

unscheduled) as the resolution date. For partial onset and resolution dates, impute dates as described in Section 6.3.

4. When an AE matches with a course of medication, the AE is considered to be an SE, however, when AEs that are SEs occur too close together, the combined AEs are one SE. If the resolution date of one AE selected as an SE is \leq 6 days before the onset date of another AE that is an SE, then combine the AEs into one SE. There could be more than two AE combined into a single SE.
5. SEs are classified in the time period where the onset date of the SE occurs regardless of the duration of the SE.
6. For each time period, count the number of SEs for each patient and whether the patient has an SE or not. Two types of summaries will be done for the SEs (also ER visits and hospitalization) to include the following patients: (1) patients with the follow-up visit or later visit for that time period, and (2) patients from (1) and patients with any SE in the time period.

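### SAP 6.4 counts a severe exacerbation only when a steroid course is linked to an AE record, and it has no step for courses that are not linked

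*Protocol*

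**What the plan says.** **Definition.** SAP 2.1 states: "Severe exacerbation is defined as worsening of asthma symptoms requiring use of systemic corticosteroids (tablets, suspension, or injection". Protocol 8.1 A uses the same words. For subjects already on daily or alternate-day oral corticosteroids (OCS), both require a worsening that needs an increase in daily dose. Neither makes an AE record part of the definition.

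**Algorithm.** SAP 6.4 builds the endpoint from two datasets:

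- Step 1: "Filter the medication data (MEDS) to keep all courses of oral corticosteroids (CLASS3=OCS"), plus intravenous entries found by text match.
- Step 2: "Merge the medication data with the AE data by patient and AE related number (RELAENO"), matched to AENUM on the AE data.
- Steps 3 and 5: the AE's dates set the length of the severe exacerbation (SE) and the year it falls in.
- Step 4: "When an AE matches with a course of medication, the AE is considered to be an SE".
- Step 6: "For each time period, count the number of SEs for each patient and whether the patient has an SE or not".

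**Data sources.** Protocol 8.0 says of opening the AE: "It is the responsibility of the Investigator to decide when an adverse event has occurred". Protocol 6.7 has site staff actively solicit "Information on adverse events, incidences of OCS pulses for worsening of asthma symptoms" at quarterly calls and office visits. It lists severe exacerbations as an item beside AEs for both kinds of contact.

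**The concern.** The definition has two elements, a worsening and a systemic steroid. The algorithm adds two more: an AE record and a correct number joining the course to it. A course whose AE number is blank or wrong, or that was given for a flare never entered as an AE, falls out at step 2 and nothing brings it back. If the patient completed that year's follow-up and has no other linked course in it, the patient stays in the denominator as exacerbation-free.

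The proportion built this way is the sole primary endpoint, and success means that the later-year proportion is shown to be less than 20 points above Year 1. In a non-inferiority comparison, errors that pull a real difference toward zero favour passing. The tipping-point analysis in SAP 2.1.3 does not help, because it addresses patients with inadequate follow-up, whereas these patients are followed and scored negative.

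**Working it through.** **1. Definition against algorithm, for a followed patient-year**

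| Situation | Definition | SAP 6.4 |
|---|---|---|
| One course for a flare, linked to its AE | SE | SE |
| One course for a flare, AE recorded, number blank or wrong | SE | none |
| One course for a flare, no AE recorded | SE | none |
| Two courses for flares, one linked | SE | SE |
| Course linked to a non-asthma AE | none | SE |
| Unchanged maintenance OCS, no AE | none | none |

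Rows 2 and 3 are the gap. Row 5 is an error in the other direction, because step 4 does not restrict the AE to asthma.

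**2. The plan's own figures**

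Inputs from Table 1 (Protocol 6.6, SAP 2.1.2): p1 = 0.33, margin 0.20, one-sided alpha 0.05, n = 250 in Year 1 and 200 in the later year.

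Power = Φ((0.20 − (pk − p1))/SE − 1.645), with SE = √(p1(1−p1)/250 + pk(1−pk)/200).

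At pk = 0.41: SE = 0.0458 and power = Φ(0.12/0.0458 − 1.645) = 83.6%. For pk = 0.33 to 0.41 the nine values are 99.8, 99.5, 99.1, 98.3, 97.1, 95.1, 92.4, 88.5 and 83.6, against 99, 99, 99, 98, 97, 95, 92, 88 and 83 printed. Table 1 reproduces, so the sample size is not in question.

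**3. Adding the loss**

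Let m1 and mk be the shares of SE-positive subject-years with no linked course in Year 1 and Year k. The documents give neither; the values below are assumptions.

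Observed difference d = pk(1 − mk) − p1(1 − m1). It is below the true difference exactly when mk·pk > m1·p1. If both shares equal m, d = (1 − m)(pk − p1).

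The current SAP uses paired data, so I also use, with observed proportions, n = 200 pairs and an assumed within-subject correlation ρ:

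SE = √((p1q1 + pkqk − 2ρ√(p1q1·pkqk))/200), where q = 1 − p, and P(pass) = Φ((0.20 − d)/SE − 1.645).

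Example, m = 10% and ρ = 0.3: p1 = 0.297, pk = 0.477, d = 0.180, SE = 0.0401, P(pass) = Φ(0.499 − 1.645) = 12.6%.

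**4. Equal loss, true 33% to 53% (a pass is wrong and should occur 5% of the time)**

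| m | Observed difference (points) | Two-group formula | Paired formula, ρ = 0.2 / 0.3 / 0.4 | Paired simulation, ρ = 0 / 0.3 / 0.5 |
|---|---|---|---|---|
| 0 | 20.0 | 5.0% | 5.0 / 5.0 / 5.0% | 4.9 / 5.0 / 5.4% |
| 5% | 19.0 | 7.7% | 7.9 / 8.1 / 8.4% | not run |
| 10% | 18.0 | 11.4% | 11.9 / 12.6 / 13.4% | 10.8 / 12.4 / 14.0% |
| 20% | 16.0 | 22.7% | 24.5 / 26.6 / 29.3% | 21.3 / 24.5 / 28.0% |

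The paired formula holds ρ fixed after the loss. The simulation applies ρ to the true outcomes and then loses events independently.

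**5. Unequal loss, same truth, paired formula with ρ = 0.3**

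| m1 | mk | Observed difference (points) | P(pass) |
|---|---|---|---|
| 5% | 0 | 21.65 | 2.0% |
| 10% | 0 | 23.3 | 0.7% |
| 0 | 5% | 17.35 | 16.0% |
| 0 | 10% | 14.7 | 36.7% |

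At 33% to 53%, Year 1 must lose positives at more than 0.53/0.33 ≈ 1.6 times the later-year rate before the bias reverses.

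**6. Away from the margin**

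With true 33% in both years and equal m, d = 0. At 33% to 41%, equal loss of 10% moves the pass rate from 91% to 95% (ρ = 0.3). A pass is correct there, since the true increase of 8 points is inside the margin.

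**7. Courses against subject-years**

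Another linked course in the same year rescues the subject. If courses follow a Poisson distribution, 20% unlinked courses means 14% to 17% of SE-positive subject-years missed, for true proportions from 53% down to 33%.

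**The case against.** - **A steroid-treated flare is an AE by definition.** Protocol 8.0 covers any symptom that appears or worsens, and AEs are actively solicited at the scheduled follow-up contacts. A perfectly linked database would lose nothing. This stands, and it is why the size is unknown rather than shown to be large.
- **Checks exist.** Protocol 10.0 and 14.0 compare CRFs with source records, and SAP 3.2 plans data review with site queries. These may find some broken links, but none is directed at steroid courses without a matching AE.
- **The direction is not fixed.** A reader might infer that durability must look better. That needs mk·pk > m1·p1. Equal loss with no true change gives no bias, and loss concentrated in Year 1 biases the other way.
- **Nothing shows that linkage worsens with time.** A reader might infer this from five years of mostly telephone contact, but Protocol 7.3.12 and 7.3.13 give every year the same three calls and one visit. The later-year-only figures show sensitivity, not expectation.
- **The spelling note in SAP 6.4 is weak evidence.** It concerns the free-text intravenous steroid field and says nothing about AE numbers.
- **The CRFs are not in the documents.** The severe-exacerbation item may itself be captured through the AE and medication forms, so a second source cannot be assumed.
- **The opposite error exists.** Courses linked to non-asthma AEs count as SEs. If false negatives (m) and false positives (f) are each equal across years, the difference is multiplied by (1 − m − f), so the two do not cancel. If they vary by year, the net direction is unknown.
- **The SAP specifies an exact paired limit.** The figures above use normal approximations and are therefore approximate.

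**Conclusion.** The gap is certain from the text: SAP 6.4 requires an AE and a matching number, the definition requires neither, and unmatched courses have no path. Its size cannot be determined, because no link rate is given.

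If loss is equal across years and the truth is 33% to 53%, losing 5%, 10% or 20% of SE-positive subject-years raises the false-pass probability from 5% to about 8%, 11–14% or 21–29%, depending on method and correlation. These figures rest on the assumed loss, on a truth exactly at the margin, and on 200 pairs (250 and 200 subjects in the two-group version).

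The documents do not support the stronger conclusions that linkage is in fact poor, that it deteriorates, or that the result will favour durability whatever the truth. The point is worth acting on because it affects the sole primary endpoint and is cheap to close.

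**What to change.** Amend SAP 6.4 after step 2, which SAP 4.7 allows before the analyses are performed:

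1. List every systemic corticosteroid course with no matching AE. Where they are captured separately, also list every severe exacerbation or OCS pulse reported at a call or visit that the algorithm did not count.
2. Query these before database lock.
3. Count as an SE each one confirmed as treatment for asthma worsening under the existing definition. Exclude unchanged maintenance OCS, which Protocol 5.4 permits: it has an asthma indication and need have no AE, so counting every unmatched course by default would contradict the endpoint.
4. Date the SE by AE onset if an AE is then recorded, and otherwise by course start.
5. Report unmatched courses by study year, so that the direction of any bias can be seen.
6. Repeat the primary test as a sensitivity analysis that also counts unresolved unmatched non-maintenance courses as SEs.

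The cost is SAP wording, one programmed listing and some site queries. The sensitivity analysis will include a few courses of uncertain indication.
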